9.7.1.6.3 EXPLORATORY EFFICACY ANALYSES

Time to change of concomitant AD treatment will be analyzed similarly to that for time to conversion to dementia based on clinical diagnosis. Time to change of concomitant AD treatment is defined as time from randomization to the first dose increase and/or initiation of treatment with AChEI or memantine after randomization. For subjects without any change of concomitant AD treatment by the end of study, the time to change of concomitant AD treatment will be censored at the date of last assessment of concomitant medication.

The proportion of subjects with any change of concomitant AD treatment at 24 months will be analyzed similarly to that for proportion of subjects with dementia diagnosis at 24 months.

The rate of change over time (mean slope) based on change from baseline in the NPI-10 item will be analyzed in a manner similar to that used for the rate of change over time (mean slope) based on change from baseline in the CDR-SB.

The analysis of the following exploratory efficacy endpoints will be performed to compare elenbecestat (E2609) versus placebo using the appropriate prespecified statistical methods including MMRM model, analysis of covariance model (ANCOVA), etc. For each exploratory efficacy endpoint, the treatment effect for elenbecestat (E2609) 50 mg per day versus placebo will be tested at a significance level of 2-sided alpha = 0.05.

- Change from baseline in NPI-10 item at 24 months
- Change from baseline in EQ-5D (subject self-reported, study partner self-reported, and subject measured by proxy) and QOL-AD (subject and study partner) at 24 months
- Change from baseline in Zarit's Burden Interview at 24 months

Additional analyses may be performed as needed.

9.7.1.7 Pharmacokinetic, Pharmacodynamic, Pharmacogenomic, and Other Biomarker Analyses

9.7.1.7.1 PHARMACOKINETIC ANALYSES

Safety Analysis sets will be used for individual elenbecestat (E2609) plasma and CSF concentration listings. The PK Analysis Set will be used for the summaries of elenbecestat (E2609) plasma and CSF concentrations.

A population PK approach will be used to characterize the PK of elenbecestat (E2609). The effect of covariates (ie, demographics) on elenbecestat (E2609) PK will be evaluated. The PK model will be parameterized for clearance (CL) and volumes of distribution. Derived exposure parameters such as AUC will be calculated from the model using the individual posterior estimate of CL and dosing history.

9.7.1.7.2 PHARMACOKINETIC-PHARMACODYNAMIC

The PK/PD relationship between CSF biomarker levels and plasma PK parameters or CSF concentrations of elenbecestat (E2609) will be explored graphically and any emergent relationship will be explored through population PK/PD modeling. These PK parameters include maximum observed concentration (C_{max}), and $AUC_{(0-24)}$ derived from the population PK model. The PK/PD relationship between plasma PK parameters and CSF concentrations of elenbecestat (E2609) with other biomarkers may also be explored using similar methods.

Additionally, the relationship between various PK parameters (eg, C_{max}) or CSF concentrations of elenbecestat (E2609) and CDR-SB at 24 months, and the relationship between various PK exposure parameters or CSF concentrations of elenbecestat (E2609) and the change from Baseline for 24 months in ADAS-cog₁₄, and the MMSE, will be explored graphically. Any emergent relationships will be explored through population PK/PD modeling. The relationship between exposure to elenbecestat (E2609) and most frequent AEs will also be explored.

9.7.1.7.3 PHARMACODYNAMIC, PHARMACOGENOMIC, AND OTHER BIOMARKER ANALYSES

The analysis of the biomarker endpoints defined as below will be performed to compare elenbecestat (E2609) versus placebo using the appropriate prespecified statistical methods including MMRM model, analysis of covariance model (ANCOVA), etc. These analyses will be conducted without adjustment for multiplicity or sequential testing. For each endpoint, the treatment effect for elenbecestat (E2609) 50 mg per day versus placebo will be tested at a significance level of 2-sided alpha = 0.05.

- Change from baseline in amyloid PET SUVR composite at 24 months for brain amyloid levels
- Change from baseline in CSF biomarkers t-tau and p-tau at 24 months
- Change from baseline in CSF amyloid biomarkers $A\beta(1-42)$, and $A\beta(1-x)$ at 24 months (revised per Amendment 03)
- Change from baseline in total hippocampal volume at 12 and 24 months using vMRI
- Change from baseline in the preservation of connectivity on fMRI from predefined anatomical regions connectivity maps (eg, precuneus, inferior frontal sulcus)

The relationship between exposure (in CSF, plasma) of elenbecestat (E2609) with potential biomarkers of Alzheimer's disease as deemed appropriate will be evaluated using appropriate statistical model with the continuous changes in biomarker at 24 months as response variables and exposure variables (in CSF, plasma) of elenbecestat (E2609) as independent variables.

9.7.1.8 Safety Analyses

Evaluations of safety will be performed on the Safety Analysis Set. The incidence of AEs, out-of-normal-range laboratory safety test variables, abnormal ECG findings, and out-of-range vital signs, suicidality, results of the sleep questionnaire, along with change from baseline in laboratory safety test variables, ECGs, and vital sign measurements will be summarized by treatment group.

9.7.1.8.1 EXTENT OF EXPOSURE

The Duration of exposure to study drug will be summarized as cumulative extent of exposure in categories with 3-month increment. The cumulative number and percent of subjects in each applicable exposure category will be presented by treatment group. Duration of exposure will be summarized using descriptive statistics as well as by 3-month duration categories using counts. The number and percent of subjects within each duration category will be presented by treatment group. Overall exposure (number of subject-months) is defined as summation over all subjects' exposure durations and will be summarized by treatment group.

9.7.1.8.2 ADVERSE EVENTS

The AE verbatim descriptions (investigator terms from the eCRF) will be classified into standardized medical terminology using the Medical Dictionary for Regulatory Activities (MedDRA). AEs will be coded to the MedDRA (Version 19.0 or higher) lower level term closest to the verbatim term. The linked MedDRA PT and primary system organ class (SOC) are also captured in the database.

A TEAE is defined as:

- An AE that emerges on or after start of study treatment, having been absent at pretreatment (Baseline) or
- Reemerges on or after start of study treatment, having been present at pretreatment (Baseline) but stopped before treatment, or
- Worsens in severity on or after start of study treatment relative to the pretreatment state, when the AE is continuous. (revised per Amendment 03)

Only those AEs that are treatment-emergent will be included in summary tables. All AEs, treatment-emergent or otherwise, will be presented in subject data listings.

The TEAEs will be summarized by treatment group on the Safety Analysis Set. The incidence of TEAEs will be reported as the number (percentage) of subjects with TEAEs by SOC and PT. A subject will be counted only once within an SOC and PT, even if the subject experienced more than 1 TEAE within a specific SOC and PT. The number (percentage) of subjects with TEAEs will also be summarized by maximum severity (mild, moderate, or

severe). The number (percentage) of subjects with TEAEs will also be summarized by relationship to study drug (Yes [related] and No [not related]).

The number (percentage) of subjects with treatment-related TEAEs will be summarized by SOC and PT. Treatment-related TEAEs include those events considered by the investigator to be related to study drug. The number (percentage) of subjects with treatment-related TEAEs will also be summarized by maximum severity (mild, moderate, or severe).

AEs will be summarized by the following subgroups: region, prior treatment with AChEIs or memantine (no or yes), and clinical subpopulation (MCI due to AD or the early stages of AD).

The number (percentage) of subjects with TEAEs leading to death will be summarized by MedDRA SOC and PT for each treatment group. A subject data listing of all AEs leading to death will be provided. The number (percentage) of subjects with treatment-emergent SAEs will be summarized by MedDRA SOC and PT for each treatment group. A subject data listing of all SAEs will be provided. The number (percentage) of subjects with TEAEs leading to discontinuation from study drug will be summarized by MedDRA SOC and PT for each treatment group. A subject data listing of all AEs leading to discontinuation from study drug will be provided.

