9.1.2.2 Follow-Up Period

All subjects, regardless of whether they complete all 24 months of treatment or discontinue study drug prematurely, will complete 2 post-treatment Follow-Up Visits; one 4 weeks after the last dose of study drug and a second 12 weeks after the last dose of study drug (Visit 14 and Visit 15 respectively). If clinically indicated, more frequent safety assessments can be made as unscheduled (UNS) assessments or visits during the post-treatment follow-up period.

In some cases, UNS visits will be needed to follow-up on safety or other findings, and the related assessments (outlined in the Schedule of Assessments) will depend on the reason for the UNS visit, and will be decided at the discretion of the investigator.

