In the event that a subject develops moderate to severe oral or genital herpes, study drug administration should be interrupted for a maximum period of 4 weeks. Subjects who develop a mild case of oral or genital herpes may remain on study drug even if the event lasts more than 72 hours. Subjects who recover from moderate to severe oral or genital herpes within 4 weeks may resume treatment if it is deemed appropriate by the investigator after consultation with the Medical Monitor. Subjects should permanently discontinue study drug if the oral or genital herpes has not resolved within 4 weeks or returns during rechallenge. (revised per Amendment 02)

Subjects who discontinue study drug early must complete the ED Visit (within 7 days of the last dose of study drug) and the Follow-Up Visits (1 and 3 months after the last dose of study drug). These Follow-Up Visits will be conducted to monitor efficacy and safety parameters after early withdrawal from the study or discontinuation of study drug.

All subjects who discontinue study drug before reaching 12 months of treatment will also be asked to return to the clinic for a 12-month clinical assessment and then again at 24 months. Subjects who discontinue treatment between 12 and 24 months of treatment will be asked to return to the clinic for a 24 month clinical assessment. Subjects who discontinue early from study drug are considered “on study” as long as they continue to return for their regularly scheduled clinical assessments at 12 and 24 months as outlined above, at which efficacy and quality of life will be assessed along with concomitant medications and AEs. However, subjects who discontinue study drug early are not considered to have ‘completed’ the study as a final Subject Disposition.

The primary reason for discontinuation and all other reason(s) contributing to the subject's discontinuation from study drug(s) should be collected on the ED from study drug electronic case report form (eCRF) page. In addition, the date of last dose of study drug(s) will be recorded on the Study Drug Dosing eCRF page. If a subject discontinues study treatment and the study at the same time, the end-of-study procedures (Final Visit) will be followed (see [Section 9.5.5](#)).

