9.5.1.5.1 ADVERSE EVENTS AND EVENTS ASSOCIATED WITH SPECIAL SITUATIONS

An AE is any untoward medical occurrence in a subject or clinical investigation subject administered an investigational product. An AE does not necessarily have a causal relationship with the medicinal product. For this study, the study drug is elenbecestat (E2609).

The criteria for identifying AEs in this study are:

- Any unfavorable and unintended sign (including an abnormal laboratory finding), symptom, or disease temporally associated with the use of an investigational product, whether or not considered related to the investigational product (Note: Every sign or symptom should not be listed as a separate AE if the applicable disease [diagnosis] is being reported as an AE)
- Any new disease or exacerbation of an existing disease

- Any deterioration in nonprotocol-required measurements of a laboratory value or other clinical test (eg, ECG or x-ray) that results in symptoms, a change in treatment, or discontinuation of study drug
- Recurrence of an intermittent medical condition (eg, headache) not present pretreatment (Baseline)
- An abnormal laboratory test result should be considered an AE if the identified laboratory abnormality leads to any type of intervention, withdrawal of study drug, or withholding of study drug, whether prescribed in the protocol or not.

All AEs observed during the study will be reported on the eCRF. All AEs, regardless of relationship to study drug or procedure, should be collected beginning from the time the subject signs the study ICF through the last visit (Visit 15, as shown in [Table 4](#)). Subjects who fail screening primarily due to AE(s) must have the AE(s) leading to screen failure reported on the Screening Disposition eCRF and the Adverse Event eCRF. SAEs will be collected for 12 weeks after the last dose.

Abnormal laboratory values should not be listed as separate AEs if they are considered to be part of the clinical syndrome that is being reported as an AE. It is the responsibility of the investigator to review all laboratory findings in all subjects and determine if they constitute an AE. Medical and scientific judgment should be exercised in deciding whether an isolated laboratory abnormality should be classified as an AE. Any laboratory abnormality considered to constitute an AE should be reported on the Adverse Event eCRF.

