9.7.2 Determination of Sample Size

The sample size for this study is estimated based on comparison of elenbecestat (E2609) versus placebo with respect to the primary efficacy endpoint, the change from baseline CDR-SB at 24 months. Based on available ADNI data [amyloid positive, MMSE equal or greater than 24, late MCI (global CDR=0.5) populations from ADNI, ADNI 2 and ADNI GO] the mean and the standard deviation of the change from baseline in the CDR-SB at 24 months in the placebo group are assumed to be 1.75 and 2.05, respectively. Therefore, assuming a 25% reduction in the mean change from baseline CDR-SB at 24 months for the elenbecestat (E2609) 50 mg per day dose group compared to placebo with a common standard deviation of 2.05 and an estimated 30% dropout rate in this study, a total sample size of 1330 subjects, 665 subjects in each treatment group, will be required to detect the treatment difference between elenbecestat (E2609) 50 mg per day and placebo using a 2-sample t-test with 90% power at a significance level of 2-sided $\alpha=0.05$.

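### Section 9.7.1.8.2 summarizes adverse events only as crude percentages of subjects; if drug stops or loss to follow-up are unequal, a true excess is attenuated and a modest one can be masked

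*Protocol*

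**What the plan says.** Protocol Section 9.7.1.8.2 fixes the measure: "The incidence of TEAEs will be reported as the number (percentage) of subjects with TEAEs by SOC and PT". A subject counts once per term. The tables by severity, by relationship to drug, and for deaths, serious events and discontinuations have the same form. No rate per unit of time, cumulative incidence or time-to-event analysis of adverse events is named.

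Section 9.7.1.8.1 does compute time on drug: "Overall exposure (number of subject-months) is defined as summation over all subjects' exposure durations and will be summarized by treatment group". It is summarized and not used further. Section 9.7.1.7.2 relates exposure to the most frequent adverse events, but that is drug concentration, not time.

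The sample size in Section 9.7.2 allows for "an estimated 30% dropout rate in this study", with no split by arm.

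Three provisions govern how long events are recorded:

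- The treatment-emergent definition, as revised by Amendment 03, begins with "An AE that emerges on or after start of study treatment, having been absent at pretreatment (Baseline) or" and has no closing date.
- Under Section 9.5.1.5.1, adverse events "should be collected beginning from the time the subject signs the study ICF through the last visit", which is Visit 15. For every subject, including early stoppers, Section 9.1.2.2 schedules two follow-up visits, "one 4 weeks after the last dose of study drug and a second 12 weeks after the last dose of study drug".
- Section 9.3.3 asks early stoppers to return at 12 months (if they stopped before then) and at 24 months, when "efficacy and quality of life will be assessed along with concomitant medications and AEs".

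**The concern.** A crude percentage compares arms fairly when both are observed for about the same time. Section 9.3.3 requires permanent stops for a second confirmed Grade 2 or greater lymphocytopenia within 6 months, seizures, moderate or severe hepatic impairment, suspected drug rash, and infection, rash or moderate to severe herpes that does not resolve. Section 7.1 names drug rash and orolabial herpes relapse among the events of interest in the multiple-dose study. It also reports some reduction in CD4 counts at 50 to 100 mg, and the trial dose is 50 mg. More stopping on elenbecestat is therefore plausible.

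If it happens, that arm accrues less time on drug, and less time under observation to the extent that stoppers do not return. Later events are then recorded less often there, and the comparison moves toward no difference. What is at stake is the reading of a small or moderate excess of later-onset events in a trial that Section 7 describes as pivotal for registration.

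**Working it through.** **Figure in the plan.** The protocol gives no adverse event rate to reproduce. Its only relevant number is the 30% dropout, and the sample size built on it reproduces: 2 × (1.960 + 1.282)² × 2.05² / 0.4375² = 461.4, so 462 per arm; 462 / 0.70 = 660 per arm against 665 stated. The 30% is one overall figure for the efficacy calculation.

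**Assumptions (not in the documents).** Constant hazards; permanent stops spread uniformly over 24 months, with share s in an arm; placebo 24-month risk p = 10%, varied from 2% to 30%; rate ratio R while on drug and the background rate off drug. The monthly background rate is λ = −ln(0.90)/24 = 0.00439. Mean time on drug is 24(1 − s/2): 21.6 months at s = 20% and 19.2 at s = 40%, a ratio of 0.89.

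**Three observation rules.** Put x = 24Rλ.

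- (a) Observation ends at last dose: risk = 1 − [s(1 − e^−x)/x + (1 − s)e^−x].
- (b) Observation ends 3 months after last dose: the event-free probability in (a) is multiplied by e^−3λ = 0.987 in both arms.
- (c) Everyone is observed to month 27: placebo risk is 1 − e^−27λ; in the active arm, stoppers revert to λ after the last dose.

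**Results, p = 10%, stops 20% vs 40%, R = 1.3**

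| Rule | Placebo | Elenbecestat | Crude ratio |
|---|---|---|---|
| (a) | 9.02% | 10.30% | 1.14 |
| (b) | 10.21% | 11.47% | 1.12 |
| (c) | 11.18% | 13.39% | 1.20 |

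If half the stoppers are seen only for 3 months and half to month 27, the crude ratio is 1.16.

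With equal stops of 30% in each arm, R = 1.3 shows as 1.28 (a), 1.24 (b) and 1.21 (c). Unequal stopping therefore explains most of the loss under (a) and (b). Under (c) nearly all of the dilution comes from off-drug time, which is present with equal stopping too.

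**Break-even R, at which the crude percentages are equal**

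| Stops, placebo vs elenbecestat | (a) or (b), p = 2% | p = 10% | p = 30% | (c), any p |
|---|---|---|---|---|
| 20% vs 30% | 1.06 | 1.06 | 1.07 | 1.00 |
| 20% vs 40% | 1.13 | 1.13 | 1.14 | 1.00 |
| 15% vs 45% | 1.20 | 1.20 | 1.22 | 1.00 |
| 10% vs 50% | 1.27 | 1.28 | 1.30 | 1.00 |

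Rules (a) and (b) share a break-even because (b) multiplies both arms by the same factor. At p = 10%, a rate ratio of 2.0 still shows as 1.45 to 1.80 in all four scenarios.

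**Matched rate.** Under (a) with 20% vs 40% and R = 1.3, on-treatment first events over time to first event or stop are 0.0902/20.54 = 0.00439 and 0.1030/18.05 = 0.00571 per month, a ratio of 1.30. The true ratio is recovered.

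**Mismatched rate.** With no drug effect and full follow-up, both arms have 11.18% with an event. Dividing by months on drug gives a ratio of 21.6/19.2 = 1.125, an excess that does not exist.

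**The case against.** **It belongs to the analysis plan.** Exposure-adjusted tables are often specified there, that plan is not shown, and Section 9.7.1.8.2 excludes nothing. This stands as a limit on scope: nothing here establishes what the trial will finally report. But the protocol states its measure outright, whereas for the per-protocol criteria and the secondary hierarchy it defers to the analysis plan in so many words. Improving a stated method is a fair request.

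**Stopping drug is not stopping observation.** This largely stands. Every stopper has visits to 12 weeks after the last dose, those who return are assessed at 12 and 24 months, and the open definition counts their events. Yet after Visit 15 they are only asked to return, and the Table 4 footnote on early discontinuation lists no laboratory sampling or physical examination for those visits. Rule (c) is a best case.

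**The imbalance may be small.** Lymphocytopenia, severe infection, most rash, and moderate to severe herpes first lead to interruptions of at most 4 weeks, each 4/104 = 3.8% of planned treatment. The CD4 reduction at 50 to 100 mg is modest; counts near or below normal are described at 200 and 400 mg. This stands, and it is why unequal stopping is a possibility only.

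**Some events cannot be hidden this way.** A first rash, seizure or lymphocytopenia is recorded before the stop that it triggers. This stands; the concern is with other and later events.

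**Readers would see an imbalance.** Exposure and disposition are tabulated by arm, and the data safety monitoring board reviews cumulative safety data. That would alert a reader to the problem but would not give a corrected comparison.

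**Conclusion.** The point holds in a limited form. As written, the protocol offers crude percentages only. If stopping or loss to follow-up is unequal, they attenuate a true excess and can mask a modest one: up to a rate ratio of about 1.13 with assumed stops of 20% vs 40%, and about 1.06 to 1.30 across the range examined. That requires observation to end at, or 12 weeks after, the last dose. With full follow-up the excess is diluted and not hidden.

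The sizes rest on assumed stop shares, constant hazards and a return to background rate off drug. The documents supply none of these.

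A reader might infer three stronger things that the documents do not support:

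- That a real excess of any size could vanish. Large excesses remain visible.
- That mandated stops end the recording of events. Sections 9.1.2.2, 9.3.3 and 9.5.1.5.1 continue it.
- That all treatment-emergent events should be divided by the subject-months of Section 9.7.1.8.1. Those are months on drug, while the definition includes off-drug events, so the rate would be inflated in the arm that stops more.

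The change should be made; it does not call the trial's design into question.

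**What to change.** In Section 9.7.1.8.2, keep the crude tables and add first-event rates by system organ class and preferred term, with numerator and denominator matched. Either pairing will do, if named in advance:

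- on-treatment first events over on-treatment time to first event or end of treatment; or
- all treatment-emergent events over time under observation to first event or last adverse event assessment.

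For selected later-onset events such as infections, herpes and malignancy, add cumulative incidence by arm with a rate ratio and 95% confidence interval. If the analysis plan already contains these, a cross-reference is enough.

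The cost is a few extra tables from data already collected. The downside is that a rate assumes a roughly constant hazard; the cumulative incidence curves check this for the selected events.
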